21.3 Adverse Event and Serious Adverse Event Classifications

Study Drug Relatedness

The following classifications should be used when evaluating the relationship of AEs or SAEs to study treatment (Table 21-1).

Table 21–1: Adverse Event Relationships

Relationship	Definition
Not Related	No relationship between the experience and the administration of study treatment; related to other etiologies such as concomitant medications or subject’s clinical state.
Unlikely Related	The current state of knowledge indicates that a relationship is unlikely.
Possibly Related	A reaction that follows a plausible temporal sequence from administration of the study treatment and follows a known response pattern to the suspected study treatment. The reaction might have been produced by the subject’s clinical state or other modes of therapy administered to the subject.
Related	A reaction that follows a plausible temporal sequence from administration of the study treatment and follows a known response pattern to the suspected study treatment and can be confirmed with a positive re-challenge test or supporting laboratory data.

Severity Assessment

For purposes of consistency, if required the investigator may use the intensity grades presented in [Table 21-2](#).

Table 21–2: Adverse Event Severity Grades

Grade	Definition
Mild	Does not interfere with subject's usual function and activities
Moderate	Interferes to some extent with subject's usual function and activities
Severe	Interferes significantly with subject's usual function and activities

If an AE increases in severity (eg, from moderate to severe); decreases in severity (eg, changes from moderate to mild); or there is a change in seriousness, a new AE will be opened and the original AE will be closed. If an AE is still ongoing at the time of a subject’s completion of the follow-up visit, the resolution/stop date and time is left blank.

To ensure there is no confusion or misunderstanding of the difference between the terms “serious” and “severe,” which are not synonymous, the following note of clarification is provided:

The term “severe” is used to describe the intensity (severity) of a specific event (as in mild, moderate, or severe myocardial infarction); the event itself, however, may be of relatively minor medical importance (such as a severe headache). This is not the same as “serious,” which is based on the subject/event outcome or action criteria usually associated with events that pose a threat to a subject's life or functioning. Seriousness (not severity) serves as a guide for defining regulatory reporting obligations.

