21.2 Definitions

Adverse Event

An AE is any untoward or undesirable medical occurrence in a subject who is administered IMP, which does not necessarily have to have a causal relationship with this treatment.

Examples of AEs include but are not limited to:

- Clinically significant laboratory findings.
- Clinically significant changes in physical examination findings.
- An AE occurring due to IMP overdose whether accidental or intentional.

- An AE occurring from IMP abuse.
- An AE associated with IMP withdrawal.
- Unexpected Adverse Event.

An unexpected AE is defined as an AE, the nature and severity of which is not consistent with the applicable product information in the most recent version of the Investigator's Brochure.

Serious Adverse Event

An SAE is defined as any untoward medical occurrence that at any dose results in any of the following outcomes:

- Death.
- A life-threatening AE.
- Inpatient hospitalization or prolongation of existing hospitalization.
- A persistent or significant incapacity or substantial disruption of the ability to conduct normal life functions.
- Results in a congenital anomaly/birth defect.

Important medical events that may not result in death, be life-threatening, or require hospitalization may be considered serious when, based upon appropriate medical judgment, may jeopardize the subject or subject and may require medical or surgical intervention to prevent one of the outcomes listed above. Examples of such medical events include allergic bronchospasm requiring intensive treatment in an emergency department or at home, blood dyscrasias or convulsions that do not result in inpatient hospitalization, or the development of drug dependency or drug abuse.

Death

Death is an outcome of an event. The event that resulted in death should be recorded and reported on the SAE Form. All causes of death must be reported as SAEs. The investigator should make every effort to obtain and send death certificates and autopsy reports to Mallinckrodt.

Life-Threatening Event

A life-threatening event refers to immediate risk of death as the event occurred per the reporter. A life-threatening event does not include an event that, had it occurred in a more

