21.4 Adverse Event and Serious Adverse Event Recording and Reporting

AEs and SAEs will be recorded from signing of the ICF through completion of the follow-up visit. The investigator is required to record the AE or SAE regardless of the severity of the event or its relationship to study treatment. Prior to the Baseline Visit/Visit 2, only AEs and SAEs related to study procedures will be recorded. The investigator must follow up on all AEs and SAEs reported to have occurred 30 days after study completion until the event has resolved or stabilized or at such time the investigator refers the subject to a nonstudy physician. The investigator will document the further follow-up information in the subject's source document.

During the period specified above, the investigator will:

- Record all AEs and SAEs from the signing of the ICF through the completion of the End of Study/Early Termination visit.
- Report all SAEs on an SAE Report Form to Global Pharmacovigilance.
- Report all pregnancies to Global Pharmacovigilance on the Pregnancy Surveillance Form.
- Submit any Expedited Safety Report or Suspected Unexpected Serious Adverse Reaction from Global Pharmacovigilance to the IRB/IEC.

The reporting requirements for AEs are summarized in [Table 21-3](#).

Table 21–3: Reporting Requirements for Adverse Events

Seriousness	Reporting Time	Type of Report
All Serious	Within 24 hours of first knowledge of event	Initial report on the SAE Form, appropriate eCRF, and source document
	Within 24 hours of receipt of follow-up information	Follow up report on the SAE Form, appropriate eCRF, and source document
Nonserious	Per case report form submission procedure	Appropriate eCRF and source document

Adverse Events

Adverse events can be reported spontaneously or elicited during open-ended questioning (ie, "How have you been feeling since your last visit?"), examination, or evaluation of a subject. Signs and symptoms must be recorded using standard medical terminology. For subjects

incapable of giving consent, the legally acceptable representative may provide information regarding the subject's status.

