25.1 Study and Study Site Discontinuation Criteria

The sponsor, investigator, or local and national regulatory authorities may discover conditions during the study that indicate that the study or study site should be terminated. This action

may be taken after appropriate consultation between the sponsor and investigator. Conditions that may warrant termination of the study/study site include, but are not limited to:

- The discovery of an unexpected, serious, or unacceptable risk to the subjects enrolled in the study.
- The decision on the part of the sponsor to suspend or discontinue testing, evaluation or development of the IMP.
- Failure of the investigator to enroll subjects into the study at an acceptable rate.
- Failure of the investigator to comply with pertinent regulations.
- Submission of knowingly false information from the study site to the sponsor, study monitor, or local and national regulatory authorities.
- Insufficient adherence to protocol requirements.
- Study/study site termination and follow-up will be performed in compliance with Mallinckrodt standard operating procedures.

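### Table 21-1 makes a known response pattern a condition of both positive causality ratings, so a well-timed reaction of a new kind fits neither and its attribution to study drug is impaired

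*Combined protocol and SAP*

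**What the plan says.** Section 21.3 introduces Table 21-1 as the classification that investigators should use for causality. The severity grades in the same section are optional by comparison. The table has four categories.

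- *Not Related*: "No relationship between the experience and the administration of study treatment; related to other etiologies such as concomitant medications" or the subject's clinical state.
- *Unlikely Related*: "The current state of knowledge indicates that a relationship is unlikely".
- *Possibly Related*: the reaction "follows a plausible temporal sequence from administration of the study treatment and follows a known response pattern to the suspected study treatment". The definition adds that the clinical state or other therapy might also have produced it.
- *Related*: the same core condition, and in addition the reaction "can be confirmed with a positive re-challenge test or supporting laboratory data".

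Section 21.2 treats expectedness as a separate idea: "An unexpected AE is defined as an AE, the nature and severity of which is not consistent with the applicable product information" in the current Investigator's Brochure. Section 21.4 assumes that some events will be both suspected and unexpected, because investigators are told to "Submit any Expedited Safety Report or Suspected Unexpected Serious Adverse Reaction from Global Pharmacovigilance to the IRB/IEC".

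The rating is used in three places. Section 20.3.6.1 summarizes AEs by causal relationship. One criterion for an AE of special interest in 21.5, and one treatment-discontinuation criterion in 15.3.1, apply to AEs of at least moderate intensity that are rated as related.

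**The concern.** Causality (did the drug cause this?) and expectedness (is this already described for the drug?) are separate judgements, and a suspected unexpected reaction needs a positive answer to the first and a negative answer to the second. Table 21-1 builds part of the second into the first: an event must resemble something already known before it may be called even possibly related.

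A relationship table is then least informative for the reactions one would most want it to show. Part 1 has no control arm, so for its AEs there is no between-group contrast to fall back on, and the reader leans on the investigators' ratings. Subjects also take a corticosteroid together with a biologic DMARD, or with methotrexate plus another DMARD (12.1). The Acthar experience in RA cited in 9.1 is thin: a preliminary open-label evaluation, an interim report on 10 subjects and a series of 5 patients. Concomitant therapy and clinical state are the alternative explanations that *Not Related* offers.

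**Working it through.** No figure in the plan bears on this point, so the check is logical. It has two steps.

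**Step 1. Take a test case through Table 21-1.** The case is a reaction with plausible timing that is new in kind, so that no response pattern for it is known.

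| Category | Conditions | Does the test case meet them? |
|---|---|---|
| *Related* | timing **and** known pattern **and** re-challenge or laboratory confirmation | No: no known pattern. A positive re-challenge does not help, because it is an added condition and not an alternative |
| *Possibly Related* | timing **and** known pattern | No: no known pattern |
| *Unlikely Related* | current knowledge points away from a relationship | Only by default: absence of knowledge is not knowledge that a relationship is unlikely |
| *Not Related* | no relationship, and another cause | Only by default: nothing in the case establishes either |

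So 0 of the 2 positive categories are open, and neither negative category properly describes the event. An investigator who must choose a row is left with the negative ones.

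The gap is narrower than the whole class of unexpected events. Section 21.2 judges both nature and severity as "not consistent with the applicable product information in the most recent version" of the Investigator's Brochure. A reaction of a familiar kind but unexpected severity could be unexpected and still follow a known pattern. Only reactions new in kind are caught.

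**Step 2. Trace where the rating counts.**

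| Element | Depends on the rating? |
|---|---|
| Recording of AEs and SAEs (21.4) | No |
| SAE report to the sponsor within 24 hours (21.4) | No |
| AE listing; TEAE tables by treatment group, system organ class and preferred term (20.3.6.1) | No |
| Withdrawal for an AE judged an unacceptable risk by the investigator, sponsor or medical monitor (22.1) | No |
| AE summaries by causal relationship (20.3.6.1) | Yes |
| AEs of special interest (21.5) | 1 of 5 criteria |
| Treatment discontinuation (15.3.1) | 1 of 6 criteria |

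The last two rows show a further inconsistency. The limbs in 15.3.1 and 21.5 refer to events *possibly*, *probably* or *definitely* related. Table 21-1 has no *probably* or *definitely* category, and its top category, *Related*, is named in neither limb. How the table's ratings map onto these two limbs is therefore not defined.

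**The case against.** The strongest objection is that little in the trial's safety surveillance runs through this rating. A reader might infer from Table 21-1 that new reactions would go undetected. The documents do not support that: the first three rows of the second table show that capture, expedited notification of serious events and the main tabulations ignore causality. This objection stands in full.

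A reader might also infer that the wording undermines the study-stopping provision in 25.1, which lists "The discovery of an unexpected, serious, or unacceptable risk to the subjects enrolled in the study". That provision does not mention the site's causality rating and does not depend on it.

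Other parts of the objection stand in part.

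- *Known response pattern* is not tied to the Investigator's Brochure and could be read broadly. Section 9.5 describes effects similar to those of corticosteroids, so a class effect might qualify. This narrows the gap without closing it.
- The assignment to the negative categories is by elimination, and how investigators would actually behave is an inference. That is right, but a table with no fitting category is itself the defect.
- Section 22.1 is a backstop to 15.3.1. For 21.5, the stated consequence is follow-up until resolution or return to baseline, while ordinary AEs are followed until resolved or stabilized (16.1) or until referral to a nonstudy physician (21.4). The loss in these two limbs is therefore secondary.
- Nothing binds the sponsor to the site's rating when it decides what is a suspected unexpected reaction. Equally, the text available describes no separate sponsor assessment of causality that would correct it.
- Part 2 has a randomized placebo comparison, which does not need causality ratings. This is why the point weighs most in Part 1.

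**Conclusion.** The concern holds as a defect of attribution. Read literally, Table 21-1 offers no positive category to a plausibly timed reaction of a new kind, and this sits badly with the protocol's own concept of a suspected unexpected reaction. The direction of the error is towards under-attribution, chiefly in the summaries by causal relationship.

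Its size cannot be stated as a number of events. The exposed setting is Part 1, with about 232 subjects treated for up to 12 weeks without a comparator. That is an enrolment figure and not a count of affected AEs. The efficacy analyses are untouched.

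The conclusion rests on three assumptions: that the *and* in the two definitions is applied as written; that investigators use the table as Section 21.3 directs; and that no instruction outside the documents supplied modifies it. The point should be corrected, but it does not threaten the trial's main results.

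**What to change.** Edit two cells of Table 21-1.

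- *Possibly Related*: require plausible timing with a reasonable possibility that the study treatment caused the event, and delete the known-pattern condition.
- *Related*: keep plausible timing, and list a known pattern, a positive re-challenge and supporting laboratory data as alternative supports. This concerns how existing evidence is classified; it does not ask for anyone to be re-challenged.

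State beside the table that expectedness is a separate judgement, made against the Investigator's Brochure under 21.2.

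In the same amendment, reconcile the category names in Table 21-1 with the terms in 15.3.1 and 21.5, so that each rating maps onto those limbs without ambiguity. This is a matter of terminology and leaves the clinical rules themselves to the sponsor.

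The cost is the amendment and a short addition to investigator training. Some more AEs will be rated possibly related; how many cannot be estimated from the documents. That is the cautious direction of error in a study whose first part has no control.

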21.4 Adverse Event and Serious Adverse Event Recording and Reporting

AEs and SAEs will be recorded from signing of the ICF through completion of the follow-up visit. The investigator is required to record the AE or SAE regardless of the severity of the event or its relationship to study treatment. Prior to the Baseline Visit/Visit 2, only AEs and SAEs related to study procedures will be recorded. The investigator must follow up on all AEs and SAEs reported to have occurred 30 days after study completion until the event has resolved or stabilized or at such time the investigator refers the subject to a nonstudy physician. The investigator will document the further follow-up information in the subject's source document.

During the period specified above, the investigator will:

- Record all AEs and SAEs from the signing of the ICF through the completion of the End of Study/Early Termination visit.
- Report all SAEs on an SAE Report Form to Global Pharmacovigilance.
- Report all pregnancies to Global Pharmacovigilance on the Pregnancy Surveillance Form.
- Submit any Expedited Safety Report or Suspected Unexpected Serious Adverse Reaction from Global Pharmacovigilance to the IRB/IEC.

The reporting requirements for AEs are summarized in [Table 21-3](#).

Table 21–3: Reporting Requirements for Adverse Events

Seriousness	Reporting Time	Type of Report
All Serious	Within 24 hours of first knowledge of event	Initial report on the SAE Form, appropriate eCRF, and source document
	Within 24 hours of receipt of follow-up information	Follow up report on the SAE Form, appropriate eCRF, and source document
Nonserious	Per case report form submission procedure	Appropriate eCRF and source document

Adverse Events

Adverse events can be reported spontaneously or elicited during open-ended questioning (ie, "How have you been feeling since your last visit?"), examination, or evaluation of a subject. Signs and symptoms must be recorded using standard medical terminology. For subjects

incapable of giving consent, the legally acceptable representative may provide information regarding the subject's status.

All fields on the AE CRF page should be completed for each event with a full description of the event and date of onset/start and resolution/stop. A medical diagnosis if known, should be recorded in lieu of each individual sign and symptom associated with the diagnosis and experienced by the subject. If no medical diagnosis is known, the term used by the subject to describe the event or signs noted by the site personnel should be recorded.

Serious Adverse Events

Initial Reporting

Serious adverse events (based on FDA/ICH definition of an SAE) require immediate reporting to Global Pharmacovigilance.

- For all SAEs, the investigator, or designee, must complete the SAE Report Form with the minimum information required by FDA and ICH and fax it to Mallinckrodt at [contact] or email at [contact] within 24 hours of first knowledge of the event even if the experience does not appear to be related to the IMP.
- The investigator, or designee, will receive acknowledgement of receipt of the SAE Report Form from Mallinckrodt.
- Should the investigator or designee have any difficulty in sending the SAE Report, they may contact Mallinckrodt based on the information in the Study Operations Manual.
- If there is any doubt about whether the information constitutes an SAE, the information is to be treated as an SAE.

The investigator(s) or designee is required to submit the any Expedited Safety Report or Suspected Unexpected Serious Adverse Reaction to the responsible IRB/IEC.

The sponsor will ensure that any Expedited Safety Report or Suspected Unexpected Serious Adverse Reaction are submitted to the FDA and other regulatory agencies as appropriate.

Follow Up Reporting

The investigator or designee must complete an SAE Report Form for all follow-up information received and fax it to Mallinckrodt at [contact] within 24 hours of receipt. The investigator(s) or designee will receive acknowledgement of receipt for each SAE Report Form from Mallinckrodt.

- The investigator or designee is required to provide all related information/supporting documentation of an SAE until the SAE is resolved or stabilized or the subject has been referred to a nonstudy physician for follow-up treatment.
- The investigator(s) or designee is required to submit the Safety Alert to the responsible IRB/IEC.
- The sponsor will ensure that any Expedited Safety Report or Suspected Unexpected Serious Adverse Reaction are submitted to the FDA and other regulatory agencies as appropriate.

21.5 Adverse Events of Special Interest

AEs of special interest for this study are outlined below. Adverse events of special interest will be followed until resolution or return to baseline.

- Elevated blood pressure (defined as systolic blood pressure \geq 180 *and* diastolic blood pressure \geq 100 mm Hg).
- Hyperglycemia (HbA1c > 6.5%, or fasting plasma glucose > 126 mg/dL, or classic symptoms of hyperglycemia with random plasma glucose > 200 mg/dL).
- MedDRA System Organ Class infection/infestation of \geq moderate intensity.
- AEs considered possibly, probably, or definitely related to IMP treatment of \geq moderate intensity.
- Hy's Law cases (ALT > 3 x ULN, with total bilirubin > 2 x ULN, no initial signs of cholestasis [alkaline phosphatase within the reference range]), and no other reason can be found to explain liver injury).

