contraindication as per the United States (US) Prescribing Information for Acthar. Subjects cannot have any history of Type 1 or Type 2 diabetes, or have any clinically significant infection.	

Concomitant Medications/Nondrug Therapies:
 
Subjects must remain on their current stable doses of DMARDs and corticosteroid throughout the study. Intraarticular corticosteroids; live or live-attenuated vaccines; enteral or parenteral immunosuppressive medications including, but not limited to azathioprine, cyclophosphamide, cyclosporine, tacrolimus, mycophenolare mofetil, rituximab (or other B-cell inhibitors); and any investigational drug, device, or procedure administered as part of a research study are prohibited during this study.
 
Opioid use is allowed during the study but prohibited in the 24 hours prior to each study visit.
 
All medications (including vaccinations) and nondrug therapies (eg, blood transfusions, oxygen supplementation) received by subjects from the Screening Visit through the Follow-up Visit will be recorded.
	

Investigational Medicinal Product and Treatment Administration:
 
Acthar contains a highly purified porcine ACTH analogue currently approved by the Food and Drug Administration (FDA) in multiple indications. Acthar and its matching placebo will be supplied by the sponsor and administered SC as follows in this study:
 
Part 1 (Open Label Period):
 
Acthar 1 mL (80 U) administered 2x/week for 12 weeks.
 
Part 2 (Randomized Maintenance Period):
 
Acthar 1 mL (80 U) administered 2x/week for 12 weeks, OR Placebo 1 mL administered 2x/week for 12 weeks.
	

Efficacy Evaluations:
 
The following efficacy assessments will be evaluated: DAS28-ESR, ACR core criteria for defining RA improvement, Clinical Disease Activity Index (CDAI), Health Assessment Questionnaire-Disability Index (HAQ-DI), and the Functional Assessment of Chronic Illness Therapy- Fatigue (FACIT-F).
	

[REDACTED]
	

[REDACTED]
	

Safety Evaluations:
 
The following safety assessments will be evaluated: adverse events, physical examinations, clinical laboratory tests, pregnancy testing, and vital signs.
	

Statistical Methods:
 
Analysis Populations
 
 The Modified Intent to Treat (mITT) Population will include all enrolled subjects who receive 1 or more doses of study drug and who contribute any efficacy data to the study. 	

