12 SELECTION OF SUBJECTS

12.1 Inclusion Criteria

Subjects must meet all of the following criteria for inclusion in the study at the Screening Visit and the Baseline Visit.

1. Subjects must be adequately informed and understand the nature and risks of the study and must be able to provide a signature and date on the ICF.
2. Subjects must be ≥ 18 years of age at Screening Visit and can be male or female.
3. Female subjects must be of nonchildbearing potential (history of hysterectomy, bilateral oophorectomy, or postmenopausal with no history of menstrual flow in the 12 months prior to the Screening Visit), or if of childbearing potential must be nonpregnant, nonlactating and agree to use effective contraception with a male partner throughout study participation (through the Follow-up Visit). Acceptable forms of contraception include hormonal measures (oral contraceptive pills, contraceptive patch, contraceptive ring, injections), intrauterine devices, double barrier method (condom plus diaphragm, condom or diaphragm plus spermicidal gel or foam), and abstinence.
4. Male subjects with a female partner of childbearing potential must have been surgically sterilized (vasectomy) or agree to use a double barrier method for contraception (condom plus diaphragm, condom or diaphragm plus spermicidal gel or foam) or remain abstinent throughout their study participation (through the Follow-up Visit).
5. Subjects must meet the criteria for RA as defined by the 2010 ACR/EULAR classification at the Screening Visit ([Aletaha et al, 2010](#)).
6. Subjects must have persistently active RA defined as a DAS28-ESR > 3.2 despite treatment with required biologic/nonbiologic DMARD(s) and a corticosteroid as defined below at the Screening and Baseline Visits.

7. Subjects must have been on a corticosteroid in the 12 weeks prior to the Screening Visit and on a stable dose of 5 mg to 10 mg of prednisone (or prednisone equivalent) for 4 weeks prior to the Screening Visit.
8. Subjects must have been on 1 of the following:
 - MTX \leq 20 mg per week and 1 additional allowed biologic or nonbiologic DMARD for at least 12 weeks prior to the Screening Visit and must remain on those doses throughout the study, OR
 - One allowed biologic DMARD for at least 12 weeks prior to the Screening Visit and must remain on that dose throughout the study.

Table 12-1 Allowed DMARDs

Allowed Nonbiologic DMARDs	Allowed Biologic DMARDs

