14. Subject has had a clinically significant infection requiring intravenous administration of antibiotics and hospitalization in the 4 weeks prior to the Screening Visit.
15. Subject has known immune compromised status, including but not limited to, individuals who have undergone organ transplantation or who are known to be positive for the human immunodeficiency virus.
16. Subject has Type 1 or Type 2 diabetes mellitus (prior diagnosis of gestational diabetes mellitus is not exclusionary) or is currently taking hypoglycemic medications.
17. Subject has any solid tumor malignancy currently diagnosed or undergoing therapy, or has received therapy for any solid tumor malignancy in the 5 years prior to the Screening Visit, with the exception of treated and cured basal cell carcinoma, treated and cured squamous cell carcinoma of the skin, and treated and cured carcinoma in situ of the cervix.
18. Subject has a diagnosis of, is undergoing therapy for, or has received therapy for a hematologic malignancy in the 5 years prior to the Screening Visit.
19. Subject has current or recent (within 24 weeks prior to the Screening Visit) drug or alcohol abuse as defined in Diagnostic and Statistical Manual of Mental Disorders, Fifth Edition, Diagnostic Criteria for Drug and Alcohol Abuse ([American Psychiatric Association, 2013](#)).
20. Subject has any of the following laboratory abnormalities at the Screening Visit:
 - Hemoglobin \leq 8.0 g/dL.
 - Platelets \leq 50,000 cells/ μ L.
 - Absolute neutrophil count (ANC) \leq 1000 cells/ μ L.
 - Aspartate aminotransferase (AST), alanine aminotransferase (ALT), or total bilirubin $>$ 2 times upper limit of normal (ULN).
 - Glycosylated hemoglobin (HbA1c) $>$ 6.5%.
 - Positive Hepatitis B surface antigen (HBsAg) or Hepatitis B core antibody (HBcAb).
 - Positive Hepatitis C virus antibody (HCV) and HCV polymerase chain reaction (PCR) \geq 25 IU/mL (HCV PCR will be automatically analyzed if HCV is positive).
 - Positive or indeterminate interferon gamma release assay (IGRA).

21. Subject has any other clinically significant disease, disorder or laboratory abnormality (including those listed on the Prescribing Information Section 5: Warnings and Precautions [Mallinckrodt ARD, 2015]) which, in the opinion of the investigator (by its nature or by being inadequately controlled), might put the patient at risk due to participation in the study, or may influence the results of the study or the subject's ability to complete the study.

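### The liver special-interest category in 21.5 is narrow; a laboratory flag on ALT or AST with bilirubin, independent of cause, would be a cheap addition

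*Combined protocol and SAP*

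**What the plan says.** Section 21.5 lists the adverse events of special interest. The liver entry reads "Hy's Law cases (ALT > 3 x ULN, with total bilirubin > 2 x ULN", followed by "no initial signs of cholestasis [alkaline phosphatase within the reference range]), and no other reason can be found to explain liver injury". All four conditions must hold together, and AST is not named.

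Other parts of the protocol bear on this entry:

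- **Entry limits (12.2, criterion 20).** A subject is excluded at Screening if "Aspartate aminotransferase (AST), alanine aminotransferase (ALT), or total bilirubin" exceeds 2 x ULN. Alkaline phosphatase has no numeric limit. Criterion 21 leaves other laboratory abnormalities to the investigator's opinion.
- **Measurement (Table 7-1, 16.7, Attachment 1).** ALT, AST, alkaline phosphatase and total bilirubin are all in the chemistry panel. It is run at every scheduled visit, including Follow-up, and analysed centrally.
- **Background drugs (12.1, criteria 7 and 8; synopsis).** Every subject takes a corticosteroid and either methotrexate with "1 additional allowed biologic or nonbiologic DMARD for at least 12 weeks prior to the Screening Visit", or "One allowed biologic DMARD for at least 12 weeks prior to the Screening Visit". On study, "Subjects must remain on their current stable doses of DMARDs and corticosteroid throughout the study".
- **Causality scale (21.3, Table 21-1).** The definition of Not Related includes events "related to other etiologies such as concomitant medications".

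**The concern.** The other condition-specific entries in 21.5 (blood pressure, hyperglycemia, infection) are defined by a measurement, by symptoms, or by a coded class with an intensity grade. None requires other causes to be excluded first. The liver entry does, in a population where every subject takes other drugs that might be blamed, and no rule or adjudicator is named for that judgement. It also omits a transaminase that the protocol measures and uses at entry.

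Classification has a consequence. Events of special interest are followed until they resolve or go back to baseline, whereas 16.1 lets follow-up of other AEs end at stabilization and 21.4 also lets it end on referral to a nonstudy physician. In the text available, this entry is also the only place with a numeric liver threshold that applies after Screening. A combined transaminase and bilirubin rise that falls outside it has no other cause-independent definition by which it would be found.

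**Working it through.** The plan states no liver event rate, expected count or capture rate, so there is no figure to reproduce. The check has two parts.

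**1. What the entry does not identify, and what else might**

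| Case (bilirubin above 2 x ULN in each) | Why it falls outside the entry |
|---|---|
| AST above 3 x ULN, ALT not | Only ALT is named |
| ALT above 3 x ULN, alkaline phosphatase above range | In-range value required; a subject above range at entry cannot qualify while it stays there |
| ALT above 3 x ULN, attributed to a background drug | Another reason has been found |

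Three other routes remain:

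- **Related AEs of at least moderate intensity (21.5).** Table 21-2 grades intensity by interference with usual activities, so a symptom-free laboratory rise can be graded Mild. Table 21-1 asks for a recognised response pattern before an event is Possibly Related. Section 9.5 names no liver effect among the common reactions (the Investigator's Brochure was not available to check).
- **Ordinary AEs (16.7, 21.4).** An out-of-range value becomes an AE if the investigator judges it clinically significant.
- **Laboratory summaries (20.3.6.2).** Abnormal results are to be picked out and analysed whatever their cause, but no liver threshold or ALT-with-bilirubin combination is specified.

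The first two routes depend on judgement, and the third has no threshold.

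**2. What an observed zero could exclude**

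Input: planned enrolment of 232 (20.7), assuming all are dosed. With 0 events in n subjects, the exact upper bound is 1 - a^(1/n).

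- One-sided 95%: 1 - 0.05^(1/232) = 0.0128, or 1.28%.
- Upper end of a two-sided 95% interval: 1 - 0.025^(1/232) = 0.0158, or 1.58%.

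If the definition captures only a share s of true cases, the bound on the true rate is the figure above divided by s. The chance of no flagged case at a true rate p is (1 - s x p)^232. Both s and p = 1% are assumptions, shown only for scale.

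| Assumed s | One-sided bound | Two-sided bound | Chance of zero flagged if p = 1% |
|---|---|---|---|
| 1 | 1.28% | 1.58% | 9.7% |
| 0.75 | 1.7% | 2.1% | 17% |
| 0.5 | 2.6% | 3.2% | 31% |
| 0.25 | 5.1% | 6.3% | 56% |

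In one Part 2 arm of 52, zero events give a two-sided bound of 1 - 0.025^(1/52) = 6.8% even with full capture.

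**The case against.** The strongest reply is that the entry correctly describes a confirmed Hy's Law case, and that the rest of the safety plan catches what it leaves out. Much of this stands.

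- **Background drugs do not rule every case out.** A reader might infer that, because every subject takes a DMARD, the last clause can almost never be met. The text does not support that. It asks whether another reason is found to explain the injury, not whether one is conceivable. DMARDs were taken for at least 12 weeks before Screening, and AST, ALT or bilirubin above 2 x ULN was excluded at Screening, so a new rise on study drug is not automatically explained by them.
- **Missing this entry is not the same as being invisible.** Table 21-1 lets an event be Possibly Related even when other therapy might have caused it, so a confounded, AST-led or cholestatic case can become special interest through the related-AE entry. AEs are recorded whatever their relationship and followed, so the loss in follow-up is modest.
- **The number missed is unknown.** A reader might assume that 2.5% to 10% of subjects enter with raised alkaline phosphatase and conclude that 6 to 23 of 232 (5.8 and 23.2) can never be flagged. That share is not in the documents, the value may return to range, and these are subjects, not injuries: at an assumed 1% injury rate they represent about 0.06 to 0.23 cases.
- **A reported zero is inferred.** The available analysis text (20.3.6 to 20.3.6.4) plans no separate count of special-interest events. Section 20.1 appears in the contents but not in the text supplied, so its silence cannot be pressed. Nowhere does the available plan claim a 1.28% bound.

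What the reply does not remove is that none of the other routes combines a liver threshold with independence from judgement.

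**Conclusion.** The point holds as a specific, inexpensive improvement to safety ascertainment, not as an error that undermines the safety conclusions. The liver entry counts only ALT-led rises with in-range alkaline phosphatase and no other reason found. AST-led cases, cases with alkaline phosphatase above range and cases attributed to a required background drug fall outside it. They may be captured elsewhere, but not by any rule that is both numeric and independent of cause.

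How many would be missed cannot be stated from the documents. The bounds of 1.28% and 1.58% for 0 of 232 hold only with complete capture and with all 232 subjects dosed. The wider bounds rest on assumed capture shares and show direction, not size. The conclusion that the entry is narrow needs none of these assumptions, since it follows from the wording of 21.5 set beside 12.2, 20.3.6.2 and Attachment 1.

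**What to change.** Add to 21.5 and to the laboratory analysis in 20.3.6.2 a 'potential Hy's Law' flag and listing, programmed from the central laboratory data: ALT or AST above 3 x ULN with total bilirubin above 2 x ULN, whatever the alkaline phosphatase or suspected cause. State whether both rises must be in the same sample.

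Keep the present definition as a second step. At case review, record alkaline phosphatase and any alternative causes as descriptors, and report how many flagged cases meet the full Hy's Law definition. Section 21.5 should also say whether flagged cases carry the special-interest follow-up.

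The cost is one definition line, one flag and one listing. All the analytes are already collected, so no new scheduled samples are needed and treatment rules do not change. The downside is a few extra cases to review and describe, with any added follow-up if flagged cases are given special-interest status.
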